#### **7.1.1 Justification for Inclusion Criteria**

- 1, 4, and 5 These were set to evaluate the efficacy of the drugs in patients with type 2 diabetes mellitus.
- 2 and 3 These were set to include the subjects who would not have a significant change in their blood glucose control, which may affect the outcomes (treatment preference)
- 6 to 9 These were set as fundamental items for the study.

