### 2) Justification for dose of the drugs

Significant change in blood glucose control during the study can affect the outcomes (treatment preference of the subjects) and should be avoided. The efficacy of trelagliptin at 100 mg in lowering blood glucose level is considered equivalent to that of alogliptin at 25 mg.

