### **7.1 Inclusion Criteria**

Subject eligibility is determined according to the following criteria prior to entry into the study.

1. Subjects who have been diagnosed with type 2 diabetes mellitus
2. Subjects who are being treated with any of the following DPP-4 inhibitors for at least 8 weeks prior to the start of treatment period (Week 0).
  - ✓ Sitagliptin : 50 mg once daily
  - ✓ Alogliptin : 25 mg once daily
  - ✓ Linagliptin : 5 mg once daily
  - ✓ Teneligliptin : 20 mg once daily
  - ✓ Saxagliptin : 5 mg once daily
3. Subjects who were judged by the investigators possible to change the treatment from daily dosing of DPP-4 inhibitor shown in Inclusion Criteria 2 to study drug trelagliptin 100 mg or alogliptin 25 mg
4. Subjects whose HbA1c value measured within 8 weeks prior to the start of treatment period (Week 0) is below 10.0%
5. Subjects who responded to DTSQ (Diabetes Treatment Satisfaction Questionnaire) at the start of treatment period (Week 0)
6. Subjects who were judged by the investigators capable to understand the contents of this clinical research and comply with them
7. Subjects who are able to sign and date the Informed Consent Form before any clinical research procedure begins
8. Subjects who are at least 20 years old at the time of giving the consent
9. Subjects who are classified as outpatients

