### **7.3 Excluded Medications**

Addition of drugs or changes in dose/regimen of drugs for treatment of type 2 diabetes mellitus or concurrent medical conditions such as hypertension are not allowed. However, the drugs to treat adverse events are permitted to be used.

[Justification for excluded medications]

These were set because they would affect evaluation of primary endpoint.

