### **7.4 Subject Management**

The investigators shall instruct subjects to adhere to the following throughout the study period:

1. Adhere to the instructions or restrictions prescribed in the study period.
2. Take glucose or sucrose (sugar) if hypoglycemia symptom (hunger abnormal, feeling of weakness, trembling of hands and fingers, cold sweat, palpitations, etc.) is observed, and if symptoms continue, visit the study site promptly.
3. For research subjects of childbearing potential, give instructions to use adequate contraception. If pregnancy is discovered, have the research subject report promptly, and discontinue the research immediately.
4. Adhere to instructed prohibited concomitant drugs. When drugs are taken other than the drugs prescribed by the investigators, have the research subject report its content.
5. Regarding subjective symptoms/objective findings, have the research subject report at visit the necessary items from its contents, onset date, degree, outcome and date of outcome.

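### Protocol 6.2 and 7.1.1 rely on inclusion criteria 2 and 3 to protect the preference endpoint from glucose change, but no criterion requires other diabetes drugs to be unchanged before Week 0

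*Protocol*

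**What the plan says.** Protocol 6.2, item 2, states the risk: "Significant change in blood glucose control during the study can affect the outcomes (treatment preference of the subjects) and should be avoided". Protocol 7.1.1 then gives the purpose of two inclusion criteria: "2 and 3 These were set to include the subjects who would not have a significant change in their blood glucose control", because such a change might affect preference.

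The criteria themselves are in 7.1:
- Criterion 2: "Subjects who are being treated with any of the following DPP-4 inhibitors for at least 8 weeks prior to the start of treatment period", followed by five named drugs with their doses.
- Criterion 3: "Subjects who were judged by the investigators possible to change the treatment from daily dosing of DPP-4 inhibitor" to one of the study drugs.
- Criterion 4: "Subjects whose HbA1c value measured within 8 weeks prior to the start of treatment period (Week 0) is below 10.0" percent.

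The only rule on other diabetes drugs is in 7.3, which disallows "Addition of drugs or changes in dose/regimen of drugs for treatment of type 2 diabetes mellitus" and likewise changes for concurrent conditions. It states no period before Week 0. Section 7.4, which includes the instruction on prohibited concomitant drugs, opens with "The investigators shall instruct subjects to adhere to the following throughout the study period".

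Under 9.3.1, consent, eligibility check, randomisation and first prescription all belong to Visit 1. There is no run-in.

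**The concern.** The protocol identifies a threat to its primary endpoint and points to a safeguard that covers only part of it. Take a subject who has been on a listed DPP-4 inhibitor for a year and whose other oral agent was started a week before Week 0. That subject meets every written criterion. The qualifying HbA1c may be up to 8 weeks old and so may pre-date the change.

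Such subjects are plausible. Protocol 4.1 says most patients with type 2 diabetes take two or more drugs together, and entry is not limited to DPP-4 inhibitor monotherapy. The sponsor also recognises the mechanism elsewhere: 7.2.1 justifies excluding fixed-dose combination users partly because the resulting drug change could alter glucose.

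If glucose is still moving in the first 8 weeks and has settled in the second, an affected subject's stated preference may partly reflect which period felt better, not weekly against daily dosing. At stake are some dilution of the contrast and some loss of power.

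**Working it through.** **1. Does any rule close the gap?**

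| Rule (protocol) | What it controls | Other diabetes drugs before Week 0? |
|---|---|---|
| 7.1 criterion 2 | At least 8 weeks on a listed DPP-4 inhibitor | No |
| 7.1 criterion 3 | Investigator's view that this DPP-4 inhibitor can be replaced | No |
| 7.1 criterion 4 | One HbA1c value below 10.0%, no limit on change | No |
| 7.2 criterion 4 | No combination pill containing a DPP-4 inhibitor | No |
| 7.2 criterion 13 | Investigator discretion | No rule named |
| 7.3 | No additions or changes | No look-back stated |

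The gap is in the text. The rest concerns its consequence.

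**2. The plan's own sample size.** Inputs from protocol 13.3: 60% weekly, 20% daily, 20% no preference; two-sided 5%; 90% power; binomial test.
- Share choosing weekly among those with a preference: 0.60 / (0.60 + 0.20) = 0.75.
- Exact test of 0.5 against 0.75 with 43 such subjects: reject at 29 or more (or 14 or fewer); power 0.904.
- 43 / 0.80 = 53.75, so 54; 54 / 0.90 = 60 randomised. The plan's figures reproduce.

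**3. Pessimistic illustration (assumed, not in the documents).** A share f of subjects ignores dosing frequency and chooses purely by period. Over both sequences they split 40/40/20.
- Weekly = (1 − f) × 0.60 + f × 0.40
- Daily = (1 − f) × 0.20 + f × 0.40
- p = weekly / (weekly + daily); power from the exact test with 43 subjects, as in step 2

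| f | Weekly | Daily | Difference | p | Power |
|---|---|---|---|---|---|
| 0 | 0.60 | 0.20 | 0.40 | 0.750 | 0.90 |
| 5% | 0.59 | 0.21 | 0.38 | 0.7375 | 0.87 |
| 10% | 0.58 | 0.22 | 0.36 | 0.725 | 0.82 |
| 20% | 0.56 | 0.24 | 0.32 | 0.700 | 0.71 |

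Simulating the Fisher form of the Mainland-Gart test in SAP 5.1.1 under the same assumption gives nearly the same powers: 0.86, 0.82 and 0.72.

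**4. Milder illustration (also assumed).** Affected subjects keep their dosing preference, but their log-odds move by a fixed amount toward the second treatment. The SAP test was simulated with 27 per sequence, 80% expressing a preference, and 20,000 runs. For a shift of 1, the chance of choosing weekly moves from 0.75 to 0.891 when weekly comes second and to 0.525 when it comes first. With 10% affected, the sequence averages are 0.9 × 0.75 + 0.1 × 0.891 = 0.764 and 0.9 × 0.75 + 0.1 × 0.525 = 0.727.

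| Share affected | Log-odds shift | Power | Type I error |
|---|---|---|---|
| 0 | 0 | 0.898 | 0.032 |
| 10% | 1 | 0.889 | 0.032 |
| 30% | 1 | 0.865 | 0.032 |
| 30% | 2 | 0.782 | 0.031 |

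Type I error does not move with the drift. A shift common to both sequences is a period effect, and the Mainland-Gart comparison between sequences allows for that.

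**The case against.** **The protocol may not promise what a reader might infer.** One could read 7.1.1 as saying that only subjects with stable glucose are admitted. It does not say that: the criteria were set to include such subjects, and the context is mainly the effect of replacing one DPP-4 inhibitor with another. The statement in 6.2 sits under the justification of dose, next to the claim that the two study drugs have equivalent efficacy. On that reading, criteria 2 and 3 do much of their intended job. This stands, and it is why the point is an incomplete safeguard and not a flat contradiction. It does not close the gap, because the risk in 6.2 is worded generally and a change in another diabetes drug produces it just as well.

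**The size is assumed.** This stands. The shares are not in the documents, and a purely period-driven choice is an extreme assumption.

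**The design already copes.** A reader might infer that the primary test is biased. It is not: sequence is randomised and type I error is preserved. Only precision is at issue.

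**Investigators can refuse such subjects** under inclusion criterion 3 or exclusion criterion 13. This is a partial safeguard. It names no stability rule, and the two sites may apply it differently.

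**HbA1c.** A reader might also infer that the HbA1c results would be seriously misread. That is too strong. HbA1c is an additional endpoint, summarised without a test (protocol 13.1.5, SAP 5.3.2). It is measured afresh at Week 0 (protocol 9.3.1; SAP 3.8 takes Day -1), so the older qualifying value is not the analysis baseline. With no group off study drug, any change from Week 0 is hard to attribute whatever the entry criteria say.

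**Conclusion.** The concern holds in a limited form. The protocol treats glucose change as a threat to preference, requires only the DPP-4 inhibitor to have been in place for 8 weeks, and leaves recent changes in other antidiabetic drugs to investigator discretion. The likely effect is noise related to period, which may dilute the weekly-daily contrast.

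Its size cannot be settled from the documents. Power falls from 0.90 to between 0.87 and 0.71 if 5% to 20% of subjects are affected and choose purely by period, but only from about 0.90 to 0.89 under the milder shift in 10%. The documents do not support treating the larger losses as expected, and they give no ground for claiming a biased test or invalid HbA1c results. The case for acting is that the remedy is cheap and serves an aim the protocol states itself.

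**What to change.** Reconcile 7.1 and 7.3 with 6.2 and 7.1.1 by adding one entry condition: other drugs for type 2 diabetes were stable before Week 0. Criterion 2's 8-week window is a natural reference; the sponsor should confirm the window. The cost is one eligibility line and a few candidates delayed or excluded.

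If enrolment has begun, add to SAP 5.1.1 a supportive repeat of the primary table without subjects whose recorded treatment periods show a diabetes drug started in that window. Protocol 9.1.5 collects drug name, route, treatment period and purpose, and SAP 4.2.3 tabulates prior medication, so starts should be identifiable. Dose is not among the fields listed in 9.1.2 or 9.1.5, so dose changes would need a check against source records. The repeat table is therefore only a partial substitute and should be labelled as such. Its cost is one flag and one table, plus the source check if dose changes are to be covered.

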## 7.2 Exclusion Criteria

Subjects who correspond to any of the following criteria will not be subjects of this clinical research.

1. Subjects who have a history of taking once-weekly dosing of DPP-4 inhibitor (trelagliptin or omarigliptin).
2. Subjects who are being treated with drugs other than those for daily oral dosing for the purpose of treatment of chronic complication (for example, “BENET® Tablets 75 mg”, a therapeutic agent for osteoporosis which is administered once monthly).
3. Subjects who are being treated with twice-daily dosing of DPP-4 inhibitor (vildagliptin or anagliptin).
4. Subjects who are being treated with anti-diabetic fixed-dose combination pill contained a DPP-4 inhibitor.
5. Subjects with moderate or severe renal impairment (for example, subjects whose eGFR is below 60 mL/min/1.73m^2).
6. Subjects for whom blood sugar control by insulin preparations is desired (for example, subjects with severe ketosis, diabetic coma or precoma, type 1 diabetes mellitus, severe infection, or serious trauma before or after surgery).
7. Subjects who have a history of hypersensitivity or allergy to DPP-4 inhibitor
8. Subjects with serious heart disease, cerebrovascular disorder, or subjects with serious disease in the pancreas, blood, etc.
9. Subjects with unstable proliferative diabetic retinopathy
10. Subjects with malignant tumor
11. Subjects who are pregnant, breast-feeding, possibly pregnant, or planning to become pregnant.
12. Subjects participating in other clinical studies.
13. Subjects who have been determined as inappropriate subjects by the investigator.

### 7.2.1 Justification for Exclusion Criteria

- 1 This was set to exclude possible effects of previous experience of taking weekly DPP-4 inhibitors on the treatment preference.
- 2 This was set to exclude possible effects of previous experience of taking non-daily orally available drugs on the treatment preference.
- 3 This was set to limit the dose frequencies as explanation factor to once daily and once weekly, since vildagliptin or anagliptin is a twice daily DPP-4 inhibitor.
- 4 This was set to rule out the possibility that the drug change from combination tablet to DPP-4 inhibitor only affects the subjects' blood glucose levels or the possibility that increase of the tablets affects their treatment preference.

- 5 to 11      These were set in consideration of safety of the subjects.  
12, 13      These were set as fundamental items for the study.

### **7.3 Excluded Medications**

Addition of drugs or changes in dose/regimen of drugs for treatment of type 2 diabetes mellitus or concurrent medical conditions such as hypertension are not allowed. However, the drugs to treat adverse events are permitted to be used.

[Justification for excluded medications]

These were set because they would affect evaluation of primary endpoint.

### **7.4 Subject Management**

The investigators shall instruct subjects to adhere to the following throughout the study period:

1. Adhere to the instructions or restrictions prescribed in the study period.
2. Take glucose or sucrose (sugar) if hypoglycemia symptom (hunger abnormal, feeling of weakness, trembling of hands and fingers, cold sweat, palpitations, etc.) is observed, and if symptoms continue, visit the study site promptly.
3. For research subjects of childbearing potential, give instructions to use adequate contraception. If pregnancy is discovered, have the research subject report promptly, and discontinue the research immediately.
4. Adhere to instructed prohibited concomitant drugs. When drugs are taken other than the drugs prescribed by the investigators, have the research subject report its content.
5. Regarding subjective symptoms/objective findings, have the research subject report at visit the necessary items from its contents, onset date, degree, outcome and date of outcome.

### **7.5 Criteria for Discontinuation or Withdrawal of a Subject**

The primary reason for discontinuation or withdrawal of the subject from the study or study drug should be recorded in the case report form (CRF) using the following categories. For subjects who withdraw from the study before administration, refer to Section 9.1.11.

1. Adverse event

The subject has experienced an adverse event (AE) that requires early termination because continued participation imposes an unacceptable risk to the subject's health or the subject is unwilling to continue because of the AE.

2. Significant protocol deviation

The discovery after the first dose of study drug that the subject failed to meet protocol entry criteria or did not adhere to protocol requirements, and continued participation poses an unacceptable risk to the subject's health.

3. Lost to follow-up

The subject did not return to the clinic and attempts to contact the subject were unsuccessful. Attempts to contact the subject must be documented in the subject's source documents

4. Voluntary withdrawal

The subject (or subject's legally acceptable representative) wishes to withdraw from the study. The reason for withdrawal, if provided, should be recorded in the CRF.

Note: All attempts should be made to determine the underlying reason for the withdrawal and, where possible, the primary underlying reason should be recorded (ie, withdrawal due to an AE should not be recorded in the "voluntary withdrawal" category).

5. Study termination

The sponsor, IEC or regulatory authority terminates the study. Refer to Section 6.3.1 for details.

6. Pregnancy

The subject is found to be pregnant.

Note: If the subject is found to be pregnant, the subject must be withdrawn immediately. The procedure is described in Section 9.1.10.

7. Lack of efficacy

The investigator has determined that the subject is not benefiting from study treatment; and, continued participation would pose an unacceptable risk to the subject.

8. Others

The investigator determined to terminate the study for other reasons.

Note: The specific reasons should be recorded on the CRF.

## **7.6 Procedures for Discontinuation or Withdrawal of a Subjects**

The investigator may discontinue a subject's study participation at any time during the study when the subject meets the study termination criteria described in Section 7.5. In addition, a subject may discontinue his or her participation without giving a reason at any time during the study. Should a subject's participation be discontinued, the primary criterion for termination must be recorded by the investigator. In addition, efforts should be made to perform all procedures scheduled for the Early Termination Visit.

## 8.0 STUDY TREATMENT

This section indicates the treatment regimen of this study. See the latest package insert for details and handling of the drug.

### 8.1 Study Drug

Generic name: trelagliptin succinate

Chemical name:

2-({6-[(3R)-3-Aminopiperidin-1-yl]-3-methyl-2,4-dioxo-3,4-dihydropyrimidin-1(2H)-yl}methyl)-4-fluorobenzonitrile monosuccinate

Generic name: alogliptin benzoate

Chemical name:

2-({6-[(3R)-3-Aminopiperidin-1-yl]-3-methyl-2,4-dioxo-3,4-dihydropyrimidin-1(2H)-yl}methyl)benzonitrile monobenzoate

#### 8.1.1 Dose and Regimen

The investigators shall administer the study drugs as shown in figure 8.a.

For trelagliptin preceding group (T-A group), trelagliptin 100 mg is orally administered once weekly for 8 weeks and then alogliptin 25 mg once daily for 8 weeks. For alogliptin preceding group (A-T group), alogliptin 25 mg is orally administered once daily for 8 weeks and then trelagliptin one weekly for 8 weeks.

Table 8.a. Dose and regimen

Treatment period		
Drug	Dose	Regimen
Trelagliptin	100 mg	Once weekly, Orally
Alogliptin	25 mg	Once daily, Orally

#### 8.1.2 Overdose

An overdose is defined as a known deliberate or accidental administration of study drug, to or by a study subject, at a dose above that which is assigned to that individual subject according to the protocol.

All cases of overdose (with or without associated AEs) will be documented on an Overdose page of the CRF, in order to capture this important safety information consistently in the database. Cases of

overdose without manifested signs or symptoms are not considered AEs. AEs associated with an overdose will be documented on AE CRF according to Section 10.0.

Serious AEs (SAEs) associated with overdose should be reported according to the procedure outlined in Section 10.2.2

In the event of overdose, the subject should be treated symptomatically.

## **8.2 Allocation of the Study Drug and Administration Procedure**

The principal investigator or the designee shall access the Case Registration Web System to allocate the study subjects. The principal investigator or the designee shall notify the information required for allocation in addition to the study subject identification (ID) code. Then, drugs that should be administered to each study subject will be notified through the Case Registration Web System. The investigators shall prescribe the study drug or comparative drug according to the notification, and record the drug information (the name, dose per administration, number of daily administration and number of tablets per administration) into the CRF of each research subject.

## **8.3 Preparation and Storage of Allocation List**

The allocation responsible person (designated by the sponsor) shall create an allocation list. Information on the allocation shall be kept in a safe place and shall not be available to anyone other than authorized persons, to secure independency from the clinical research.

## **9.0 STUDY PLAN**

### **9.1 Clinical study procedure**

The investigators shall collect data in accordance with the procedure below. In principle, all the tests, observations, and evaluations of study subjects shall be performed by the same investigators. The study schedule is provided in Appendix A.

#### **9.1.1 Informed Consent Procedure**

The procedures for obtaining informed consent are described in Section 15.3.

Consent shall be obtained from the study subject before initiation of study.

A study subject ID code will be given to each study subject who provided informed consent, and then the study subject is to be de-identified. The study subject ID code shall be used throughout the study period and shall not be changed.

#### **9.1.2 Demographics and Medication History Collection Procedure**

The following data will be collected as demographic data:

- Date of birth, gender, the time (month and year) of diabetes onset (or a diabetes diagnosis), work status, alcohol intake history, smoking history, experience in educational hospitalization on diabetes, presence of cohabiter, compliance with DPP-4 inhibitors for the last 4 weeks before the start of the treatment period, the number of oral drugs per day, complication of metabolic syndrome\*.

\*: to be confirmed according to the following criteria:

waist size  $\geq 85$  cm (for male),  $\geq 90$  cm (for female)

serum triglyceride  $\geq 150$  mg/dl and/or HDL  $< 40$  mg/dl

systolic blood pressure  $\geq 130$  mmHg and/or diastolic blood pressure  $\geq 85$  mmHg

#### **9.1.3 Physical Examination Procedure**

The presence/absence of clinically significant abnormalities at subsequent physical examinations during the course of this study treatment will be determined compared with the baseline physical examination.

#### **9.1.4 Weight, Height, and Body Mass Index (BMI)**

Body weight shall be measured to one decimal place in kilograms.

Height shall be measured to the nearest whole number in centimeters.

The sponsor will calculate BMI using the formula below, showing one decimal place.

Body Mass Index:  $BMI = \text{body weight (kg)} / [\text{height(m)}]^2$

